3.8.3 Post-treatment

After treatment (non-progression end of treatment), examinations should be performed every 3 months until disease progression (see flowchart).

3.8.4 Temporary Visits

Temporary visits should be conducted based on clinical needs. Corresponding clinically significant laboratory test abnormalities and adverse events should be recorded in the CRF and original documentation. If multiple laboratory tests are performed on the same day, only one set of test values needs to be recorded in the CRF. However, all abnormal values from repeated laboratory tests should be documented in the CRF.

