3.7.2 Safety Indicators

All patients who have received at least one dose of the investigational drug will be included in the safety analysis as the valid population. The physical examination results, vital signs, adverse events, and abnormal laboratory test values of the patients will be summarized. All adverse events should be reported and graded according to the Common Terminology Criteria for Adverse Events (CTCAE) version 5.0.

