5.1.3.3 Safety Analysis

Adverse events and their most severe reaction levels will be summarized according to the criteria of the 5th edition of the NCI CTCAE. Additionally, adverse events will be summarized based on their severity and relationship with the investigational drug.

Descriptive summaries of laboratory test values primarily focus on abnormal values.

Laboratory test abnormalities will also be summarized according to the most severe level specified in the 5th edition of the NCI CTCAE.

6. Adverse Events

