6.3.5 Recording of Adverse Events

All adverse events occurring after the subject signs the informed consent form must be fully documented in the subject's case report form.

Records must be supported by original documentation. Laboratory test abnormalities deemed clinically relevant (e.g., those leading to early study withdrawal, requiring treatment, or causing significant clinical manifestations, or those considered clinically relevant by investigators) should be reported as adverse events. Each event must be described in detail, including the start and end dates, severity, relationship to the investigational product, measures taken, and the outcome of the event.

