6.4 Reporting of Serious Adverse Events

From the time of informed consent signing until 30 days after the completion of the last dose, any defined serious adverse event (SAE), including laboratory test abnormalities meeting the SAE definition, must be immediately reported to the designated personnel in the study documents (within 24 hours of the investigator's knowledge). The SAE report form must also be completed and submitted to the designated personnel in the study documents within 24 hours of the investigator's knowledge.

Each serious adverse event should be followed up until resolution or stabilization,

with an updated report submitted to the designated personnel. A simple Level 4 laboratory test abnormality (according to the CTCAE 5.0 criteria) should not be reported as a serious adverse event unless the investigator determines that the abnormality meets the International Conference on Harmonisation (ICH) criteria for serious adverse events (as defined in Section 6.3.2). A Level 4 laboratory test abnormality that occurs at baseline and is a manifestation of the disease according to the CTCAE 5.0 criteria should not be reported as a serious adverse event, particularly if the abnormality is present but the patient is still allowed to enroll or is not excluded from enrollment. If there is any doubt about whether the abnormality should be reported as a serious adverse event, the investigator may consult the study monitor. A Level 4 laboratory test abnormality should be recorded on the "Laboratory Data" page and regularly cross-checked by the medical monitor.

According to the requirements of local laws and regulations, serious adverse events must be reported to the ethics committee and the drug regulatory authority.

7. Appendix

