7.5 Research Process Table

Flowchart of Therapy Process

	pretherapy	Each 3-week period constitutes one cycle.			Post-treatment follow-up visit	Follow-up after treatment discontinuation due to non-progressive conditions until disease progression	Follow-up after progression 9
		Cycle 1	Cycle 2	The 4th and subsequent cycles until disease progression or treatment discontinuation			
Operation item	Filter period	Day 1	Day 1	Day 1	Within 7 days	Every 8 weeks	Every 3 months
Informed Consent Form	X (within 28 days)						
Medical History 1	X (within 7 days)						
Complete physical examination 2	X (within 7 days)						
Inclusion/Exclusion Criteria	X						
stochastic	X						
Life signs and ECOG score	X	X	X	X	X	X	
12-lead electrocardiogram	X (within 28 days)		X	X	X		
Brain CT or MRI scan 3	X (within 28 days)						
Imaging Evaluation 4	X (within 28 days)			X (every 6 weeks) -----			
Hematological examination 5	X (within 7 days)		X	X	X		
Complete Set of Biochemical Tests 6	X (within 7 days)		X	X	X		
Urine test 7	X (within 7 days)		X	X	X		
Fecal Test 8	X (within 7 days)			X (every 6 weeks) -----			
Serum pregnancy test	X (within 7 days)						
Study of drug use		X	X	X	X		
Evaluation of Adverse Events (AEs)				-----(
comorbidities and concomitant medications				-----(

1. Complete medical history, demographic data, surgical history, concomitant medications, comorbidities, allergy history, and smoking history.
2. Complete physical examination, ECOG performance status score, height, weight, vital signs, and detailed examinations of all body systems.

3. Head CT/MRI scans are only required for patients with baseline neurological symptoms to exclude brain metastases.
4. Tumor assessment during the treatment phase is required every 6 weeks. After treatment completion, imaging evaluations are required every 8 weeks until disease progression occurs. If a patient withdraws from the study due to disease progression, no additional CT scans are required during the final follow-up at study completion.
5. Hematological tests include: hemoglobin, hematocrit, platelets, white blood cells, absolute neutrophil count, and absolute lymphocyte count, which can be performed 1 day prior to the start of each treatment course.

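### Section 3.8.4 ties CRF entry of laboratory abnormalities at temporary visits to clinical significance, while the worst-grade laboratory summary in 5.1.3.3 has no such condition, so that summary can miss lower-grade abnormalities within a cycle

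*Protocol*

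**What the plan says.** Three sentences in Protocol section 3.8.4 govern what is recorded at temporary visits, which are made on clinical need:

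- General rule: "Corresponding clinically significant laboratory test abnormalities and adverse events should be recorded in the CRF and original documentation".
- Several tests on one day: "If multiple laboratory tests are performed on the same day, only one set of test values needs to be recorded in the CRF".
- Repeats: "However, all abnormal values from repeated laboratory tests should be documented in the CRF".

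The analysis sections carry no significance condition. Section 3.7.2 says "The physical examination results, vital signs, adverse events, and abnormal laboratory test values of the patients will be summarized". Section 5.1.3.3 says "Laboratory test abnormalities will also be summarized according to the most severe level specified in the 5th edition of the NCI CTCAE".

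Two other sections bear on the point. Section 6.3.5 uses clinical relevance to decide which laboratory abnormalities are also adverse events; its list ends with "or those considered clinically relevant by investigators) should be reported as adverse events". Section 6.4 sends Grade 4 laboratory abnormalities to the laboratory page of the CRF, with regular cross-checks by the medical monitor and no significance condition.

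In the flowchart in section 7.5, on-treatment haematology, biochemistry and urine tests are marked on Day 1 from Cycle 2 onward and at the post-treatment visit within 7 days. The haematology footnote adds "which can be performed 1 day prior to the start of each treatment course", and the biochemistry and urine footnotes say the same in substance.

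**The concern.** A worst-grade table takes, for each patient and test, the highest grade among the values in the database. It is complete only if entry of a value does not depend on what someone thinks of it. In 3.8.4 the general rule makes entry depend on investigator judgement, and the two sentences that follow lift that condition only for particular situations.

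The study is single-arm, so the investigators know the treatment. Safety is a stated secondary endpoint (sections 2 and 3.7), and the introduction presents the combination as a low-toxicity alternative to chemotherapy. A collection rule that can lower the laboratory grades, and cannot raise them, bears on that argument. The primary endpoint, ORR, is not affected.

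**Working it through.** The point rests on wording, and the protocol gives no figure to reproduce. The check sets the sections side by side.

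**Step 1. Which unscheduled values does 3.8.4 require in the CRF?**

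| Unscheduled laboratory value | Must it be entered? | Source |
|---|---|---|
| Judged clinically significant, any grade | Yes | 3.8.4, general rule |
| Abnormal, from a repeated test | Yes, whatever its significance | 3.8.4, last sentence |
| Several tests on one day | One set of values, plus abnormal values from repeats | 3.8.4, second and third sentences |
| Grade 4 | Yes, on the laboratory page | 6.4 |
| Grade 1 to 3, single unrepeated test, judged not significant | Not stated | none |

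The last row is the gap. The protocol also does not say whether a repeated test means a second sample on the same day, a re-check on a later day, or any test done before in that patient. The edge of the gap is therefore open.

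**Step 2. Do the analysis sections need the values in the last row?** Yes. Section 3.7.2 summarises abnormal values and 5.1.3.3 the most severe grade, and neither restricts this to significant values.

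**Step 3. Would scheduled samples pick up the same abnormality?** Not if it appears and recovers within a cycle. Under 3.6.1 a cycle is 21 days and anlotinib is taken on days 1 to 14. The next Day 1 is day 22 of the running cycle, so a scheduled sample falls 22 − 14 = 8 days after the last anlotinib dose, or 21 − 14 = 7 days if it is drawn the day before. The post-treatment visit within 7 days adds one sample not tied to Day 1. Values between these points reach the database only through temporary visits.

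**Step 4. Direction.** Let A be all graded post-dose values of one test in a patient and B the subset entered. Since B is contained in A, max(B) ≤ max(A). Leaving values out keeps the worst grade the same or lowers it.

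**Step 5. Size.** The documents give no rate of unscheduled tests, of laboratory abnormalities by grade, or of abnormalities judged not significant. A product of assumed rates would only return the assumptions, so none is offered. The one figure available is the unit: if all 37 planned patients are dosed, each patient whose worst grade is missed shifts a proportion by 1/37 = 2.7 percentage points.

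**The case against.** The strongest case against the point is that 3.8.4 does not exclude anything. It says that significant abnormalities should be recorded, not that other values are left out. The sentence on same-day tests presupposes that a set of values is entered, and abnormal repeats are required without condition. Elsewhere (6.3.5) clinical relevance works as a test for adverse event reporting and not as a filter on laboratory data. A site could fairly read the whole section as an instruction to enter everything. Temporary visits follow a clinical need, so many abnormal results there would be judged significant anyway. The text also reads as a rough translation, which makes it risky to infer much from one adjective. Finally, the rules for worst-grade tables are commonly left to an SAP or to CRF instructions, which are not shown.

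Much of this stands, and it limits the point to the last row of the table in the working. It does not close that row: no sentence requires entry of a single, unrepeated Grade 1 to 3 value judged not significant. An SAP can choose among collected values but cannot supply values that were never entered. Monitoring under 3.9 compares the CRF with source documents, but a value that the protocol does not require would not clearly count as a discrepancy.

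A reader might infer more: that only significant abnormalities are recorded, so that the table is filtered by opinion and does understate toxicity. The documents do not support this. The general rule in 3.8.4 does not contain the word only, and both Grade 4 values and abnormal repeats are captured regardless of significance. A reader might also set the possible shortfall against the 13.3% quoted in the introduction. That figure is the rate of treatment-related adverse events of grade 3 or higher in the preceding study. It is a different output from a laboratory worst-grade table and is no benchmark here.

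**Conclusion.** The point holds in limited form. The recording rule in 3.8.4 and the summaries in 3.7.2 and 5.1.3.3 do not match for one class of values: Grade 1 to 3 results from single, unrepeated unscheduled tests judged not clinically significant. Grade 3 is the part of that class that matters most.

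The worst-grade laboratory table can therefore miss abnormalities within a cycle, and any effect is downward or nil. This assumes that at least some sites read the general rule as a limit on entry; if all sites enter every value, nothing is lost. The size cannot be derived from the documents. Adverse event reporting under 6.3.5 and the ORR analysis are untouched. It is a defect worth correcting before enrolment because it is cheap to correct then; later, the missing values would have to be retrieved from source records.

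**What to change.** - **Section 3.8.4.** State that all laboratory results from temporary visits, or at least all abnormal ones including same-day repeats, are entered in the CRF with their date, whatever their judged significance. The undefined term for repeats then no longer decides what is entered; if it is kept, define it.
- **Section 6.3.5.** Keep clinical significance here only, as the test for whether a laboratory abnormality is also reported as an adverse event.
- **Section 5.1.3.3.** State that the worst CTCAE grade is taken over scheduled and unscheduled values after the first dose.

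The cost is an amended CRF instruction and slightly more data entry. No tests or visits are added. The laboratory table may look somewhat less favourable than it would under the present wording.

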3.8.5 Follow-up after disease progression

Contact patients every 3 months (via in-person visits or telephone calls) to obtain data on overall survival and post-study chemotherapy. Follow-up should be conducted every 3 months until the patient's death. During each follow-up visit, the following information should be collected:

- Patient survival status.
- Disease status and progress date (if applicable).
- Date of death (if applicable).
- Record all new anticancer therapies.

Note: Patients with tumor progression should be treated as other patients with advanced colorectal cancer.

3.9 Data Quality

In compliance with the guidelines of Good Clinical Practice (GCP), monitors will conduct regular visits to each center to ensure adherence to the study protocol, GCP, and relevant regulations. The visits will include on-site inspections of the completeness and clarity of Case Report Forms (CRFs), cross-verification with original documents, and clarification of management-related matters.

3.10 Archive

The data entered into the Case Report Form (CRF) must be consistent with the original documents or recorded directly in the CRF. In cases of direct recording in the CRF, the recorded content shall be considered as the original data. The parameters of the original data must be validated, and the source information of the data must be documented. Both the study documents and all original data should be retained until the investigator issues a notice for destruction.

4. Ethical and Legal Considerations

4.1 Ethics Committee (EC) or Institutional Review Board (IRB)

In accordance with Good Clinical Practice (GCP), Chinese laws and regulations, and requirements of relevant organizations, all participating centers must obtain approval documents from the corresponding ethics committee/institutional review board prior to the initiation of the study. When necessary, extensions, amendments, or re-evaluations of the ethics committee approval must be obtained and forwarded to the investigators.

4.2 Ethical Guidelines for This Study

The procedures for operations, evaluations, and documentation in this research protocol are designed to ensure that researchers adhere to the guidelines of clinical practice standards and the principles detailed in the Declaration of Helsinki. The implementation of this study will also comply with relevant laws and regulations in China.

Researchers are not permitted to modify the study protocol without prior consent. However, in emergency situations to eliminate risk factors for subjects, researchers may deviate from or alter the protocol without obtaining approval or support from the Ethics Committee/Institutional Review Board/Principal Investigator. Any deviations or modifications made, along with their rationale, must be promptly reported to the Ethics Committee/Institutional Review Board/Principal Investigator. Where appropriate, a proposal for protocol amendment should also be submitted. Researchers are required to provide a comprehensive explanation and justification for all deviations or modifications to the study protocol.

4.3 Subjects' Instructions and Informed Consent

The subject must be provided with the key information of the study and the informed consent form. Prior to the initiation of the study, the investigator must provide the subject with written approval from the ethics committee/institutional review board (IRB) or endorsement of the informed consent form, along with all other written information. The ethics committee/institutional review board approval and the approved informed consent form must be archived together in the study documentation.

Informed consent must be obtained prior to the implementation of any specific study procedure. The date of participant enrollment and signing of the informed consent form shall be recorded in the corresponding subject documentation.

4.4 Confidentiality

All records relating to the identity of the patient are kept confidential and will not be made publicly available to the extent permitted by applicable laws and/or regulations.

The names of participants will not be provided. Case report forms only record the participant's number and the initials of their name. If the participant's name appears in any other documents (e.g., pathology reports), copies of such documents must be redacted. Computer-stored research reports must comply with local data protection laws. When research results are published, participant identities will also be kept confidential.

The investigators will keep a list to identify the records of the subjects.

5. Statistical Methods

5.1 Statistical and Analysis Plan

5.1.1 Study Population Analysis

The efficacy analysis will be conducted in the intention-to-treat (ITT) population, defined as all patients who received at least 2 cycles of study drug therapy. The safety analysis population includes all patients who received at least one dose of study drug therapy. The response rate analysis population refers to all patients in the ITT population who achieved partial or complete response as determined by the RECIST criteria.

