Name of the principal investigator at the sub-center:

Signature: Date: Year Month Day

Signature: Date: Year Month Day

Sponsor/Lead Organization

corporate name		Changzheng Hospital Affiliated to Naval Medical University	
project leader		[name]	
Contact address	[name]	zip code	200003
[contact]	cellphone	[name]
portraiture	[name]	E-mail	[contact]

Cooperative Unit

Company/Unit Name		Innovent Biologics (Suzhou) Co., Ltd.	
project leader			
Contact address		zip code	
telephone		cellphone	
portraiture		E-mail	

Company/Unit Name		Chia Tai Tianqing Pharmaceutical Group Co., Ltd.	
project leader			
Contact address		zip code	
telephone		cellphone	
portraiture		E-mail	

scenario summary	
scenario name	A phase II study of anlotinib plus sintilimab as first-line treatment for advanced non-liver metastatic colorectal cancer
Program number	APICAL-CRC2
version number	1.0
date	2025-12-8
Sponsor	Shanghai Changzheng Hospital
indication	Advanced colorectal cancer
Estimated study duration	The study is scheduled from December 2025 to December 2026. Enrollment for this research project is planned to commence in December 2025 and is expected to conclude in December 2026. Data analysis will be completed in June 2026, with the total trial duration approximately 1.5 years.
purpose of research	The efficacy of anlotinib combined with sintilimab as first-line therapy for advanced non-hepatic metastatic colorectal cancer was evaluated using the investigator-assessed objective response rate (ORR).
Total number of cases	The sample size calculation was based on the margin of confidence compared with historical controls, assuming an ORR of 70% in this study and an ORR rate of 50% in the historical controls. In the ITT analysis set, according to the Simon two-stage design, with a one-sided $\alpha=0.05$ and statistical power=0.8, the calculated sample size was 37 cases.

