3.1 Research Design and Planning

This study is a prospective, single-center clinical trial employing anlotinib combined with sintilimab. Based on preliminary research findings and statistical analysis of prior literature, the planned enrollment number is 37 patients.

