3.6.2.1 Dose Adjustment

During the treatment phase of this study, the dose of the relevant drug should be

reduced or the medication should be suspended if any of the drug-induced severe toxic reactions occurs.

The dose adjustment for the next cycle will be based on the toxic reactions observed in the previous cycle.

In the event of any severe hypersensitivity reaction to the relevant medication during treatment, the injection should be immediately discontinued and documented.

If a patient develops a severe hypersensitivity reaction on day 1 of the first treatment course, the patient should be excluded from the study.

Imaging evaluation should be performed even if the patient has developed hypersensitivity to the drug, provided that at least two cycles of chemotherapy have been completed.

The specific dose adjustment was implemented according to the chemotherapy-related adverse event management guidelines and drug instructions.

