5.1.3 Efficacy Analysis

The efficacy analysis will be performed in the ITT population.

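### The efficacy population labelled ITT requires at least 2 cycles of treatment, so early failures drop out of the ORR denominator and the stated alpha and power no longer hold

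*Protocol*

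**What the plan says.** Section 5.1.1 names the efficacy population ITT but restricts it to patients who have already been on treatment for some time: it is "defined as all patients who received at least 2 cycles of study drug therapy". Section 5.1.3 confirms its use: "The efficacy analysis will be performed in the ITT population". The safety set in Section 5.1.1 needs only one dose.

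The synopsis ties the sample size to this population ("In the ITT analysis set, according to the Simon two-stage design"), "assuming an ORR of 70% in this study and an ORR rate of 50% in the historical controls", with one-sided alpha 0.05 and "statistical power=0.8, the calculated sample size was 37 cases". Section 3.1 plans to enrol the same number: "the planned enrollment number is 37 patients".

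Two further passages bear on who is counted:

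- Section 3.6.2.1: "If a patient develops a severe hypersensitivity reaction on day 1 of the first treatment course, the patient should be excluded from the study".
- Section 5.1.1 adds a third set: "The response rate analysis population refers to all patients in the ITT population who achieved partial or complete response".

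Cycles last 3 weeks (Section 3.6.1), and response is first assessed after 2 cycles, at 6 weeks (Sections 3.6.1, 3.7.3.2 and 3.8.2). The protocol has no rule counting unassessed patients as non-responders, no replacement rule, no drop-out allowance and no second efficacy set.

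**The concern.** A set that depends on treatment received after enrolment is an evaluable set, not an intention-to-treat set. Here the condition is closely tied to outcome. A patient lost before 2 cycles will usually have no scan showing a response, so the rule removes non-responders and keeps responders. The trial has no concurrent control arm in which the same selection would operate, so the inflated ORR is compared directly with a fixed 50%.

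PFS and OS are affected as well. Patients must survive and stay on treatment into cycle 2 to be counted, but the clock starts earlier: at enrolment for PFS in Section 3.7.1, and at randomization for OS there and for both endpoints in Section 5.1.3.2. That early stretch is guaranteed event-free time for everyone retained.

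There is no slack either. The 37 cases are required within the 2-cycle set but only 37 are to be enrolled, so a single early loss leaves the set short.

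**Working it through.** **Inputs.** From the synopsis: p0 = 0.50, p1 = 0.70, one-sided alpha 0.05, power 0.80, N = 37, Simon two-stage. From Section 3.1: 37 enrolled. The share d leaving before 2 cycles is not given, so 3% to 20% is assumed. The only internal hint is the earlier study in Section 1. It enrolled 30, but its 48.3% and 89.7% fit 14/29 and 26/29 (14/30 would be 46.7%). One patient of 30, about 3%, therefore appears to have been left out; this is an inference.

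**Step 1: reproduce the plan's figure.** Enumerating Simon designs exactly, the minimax design is: stop if ≤12 of 23 respond; otherwise continue to 37 and declare success if ≥24 respond. With b the binomial probability,

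P(success | p) = Σ over x from 13 to 23 of b(x; 23, p) × P(X₂ ≥ 24 − x | 14, p).

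This gives alpha 0.048 and power 0.801, so 37 is reproduced. The single-stage rule ≥24/37 gives 0.049 and 0.807. The sample size is not at fault.

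**Step 2: effect of the set.** If the share d who leave are all non-responders, the ORR among those kept is p/(1 − d). At d = 10%, 0.50/0.90 = 55.6% and 0.70/0.90 = 77.8%.

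- Rule A: accrue until 37 patients are in the 2-cycle set, then apply the minimax cut-offs.
- Rule B: enrol 37 without replacement and apply an exact one-sided 5% test to the m patients left, averaging over m ~ Bin(37, 1 − d).

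| Early loss d | True 50% appears as | True 70% appears as | Alpha, A | Alpha, B | Apparent power, A | Apparent power, B |
|---|---|---|---|---|---|---|
| 0% | 50.0% | 70.0% | 0.048 | 0.049 | 0.801 | 0.807 |
| 3% | 51.5% | 72.2% | 0.070 | 0.059 | 0.873 | 0.843 |
| 5% | 52.6% | 73.7% | 0.090 | 0.072 | 0.913 | 0.877 |
| 10% | 55.6% | 77.8% | 0.162 | 0.122 | 0.975 | 0.947 |
| 15% | 58.8% | 82.4% | 0.279 | 0.207 | 0.997 | 0.986 |
| 20% | 62.5% | 87.5% | 0.448 | 0.331 | 1.000 | 0.998 |

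**Step 3: results that flip (exact one-sided p against 50%).**

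- 22 responders: 22/37 = 59.5%, p = 0.162 (fail). Four losses removed: 22/33 = 66.7%, p = 0.040 (success).
- 23 responders: P(X ≥ 23 | 37) = 0.0494 + C(37,23)/2³⁷ = 0.0494 + 0.0444 = 0.094 (fail). Two losses removed: 23/35 = 65.7%, p = 0.045 (success).

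**Step 4: the other reading of power.** Suppose the 70% target means ORR within the 2-cycle set, so that drop-out is unrelated to response. With 37 enrolled, the exact test needs 24/36, 23/35, 23/34 or 22/33 responders, and power is 0.737, 0.773, 0.693 and 0.733 respectively, all below 0.80. The uneven pattern reflects the discreteness of the binomial.

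**The case against.** The main counter-arguments are as follows.

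- **Received is not completed.** A patient dosed on day 1 of cycle 2 may qualify, which would cut the exclusion window from about 6 weeks to about 3 and keep in anyone who then progresses at the 6-week scan. This stands: it reduces the bias but does not remove it, because losses in the first cycle still leave the set.
- **Early loss may be small.** Eligibility here (ECOG 0-1, no liver metastases, life expectancy of at least 12 weeks) is more favourable than in the earlier study, where about 1 in 30 was apparently left out. At 3.3%, alpha under rule B is 0.061. One loss cannot change the result, since 24 responders are needed at both n = 37 and n = 36. With 22 responders, three losses still fail (22/34, p = 0.061), and at that rate four or more losses among 37 have a probability of about 3%. This limits the likely size. Two losses are enough with 23 responders, however, and their chance is not small: 1 − (29/30)³⁷ − 37 × (1/30) × (29/30)³⁶ = 1 − 0.285 − 0.364 = 0.35.
- **The decision rule is assumed.** If the fixed counts (more than 12 of 23, at least 24 of 37) were applied to all enrolled patients, removing non-responders would not alter the count, and alpha would stay at 0.048. This is correct, but the protocol states no such cut-offs and places the analysis in the 2-cycle set. The ORR estimate would still be inflated.
- **Power is not lost in the main scenario.** Agreed. If the leavers are non-responders, apparent power is overstated. It falls below 0.80 only under the reading in step 4.
- **The responder-only set is probably a mislabel** for the duration-of-response analysis in Section 3.7.1. That is likely, and it is not evidence of bias in the ORR. It still needs correcting, because a response rate in that set is 100% by construction.

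**Conclusion.** The plan is wrong as written, and this should be corrected before data accrue. The population called ITT is selected on early outcome, and the protocol contains nothing that offsets the selection. The direction of the bias is certain: the ORR is overstated whenever an early leaver is a non-responder. The size depends on an early-loss share the protocol does not give and on an unstated decision rule. Even at 3% loss, real alpha exceeds 0.05 (0.059 under rule B, 0.070 under rule A); at 10% it is 0.122 to 0.162. If early loss is instead unrelated to response, the cost is power, at 0.69 to 0.77 with 33 to 36 patients left. PFS and OS carry a guarantee-time bias of roughly one to two cycles, depending on how receipt of 2 cycles is read.

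**What to change.** In Sections 5.1.1 and 5.1.3 and the synopsis:

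1. Define the primary efficacy population as all enrolled patients who received at least one dose, which is the existing safety set, and use it for ORR, PFS and OS.
2. State that patients with no post-baseline tumour assessment count as non-responders for ORR.
3. State that patients taken out under Section 3.6.2.1 for day-1 hypersensitivity remain in the efficacy denominator. This concerns the analysis only, not their clinical management.
4. Keep the 2-cycle set as an evaluable set, labelled as a sensitivity analysis, and say whether starting or completing cycle 2 qualifies.
5. Delete the response rate analysis population, or rename it the duration-of-response set.
6. State that the 37 cases and the stage cut-offs refer to the population in item 1.

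The cost is protocol wording only. N stays at 37, and with 37 patients in that population the minimax rule (stop at ≤12/23, success at ≥24/37) has alpha 0.048 and power 0.801. The reported ORR may be slightly less favourable.
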